#### *CCTA*

C- Coronary Plaque Volume/Composition via Computed Tomography Angiography: (0 and 52 weeks)

Coronary plaque volume/composition will be measured using multi-detector computed tomography. Recent studies demonstrated the computed tomography angiography can accurately measure plaque characteristics including volume and composition with high reproducibility. Furthermore, they provide evidence that CT angiography is feasible and diagnostic utilizing radiation doses as low as 2 mSv without compromise of image quality, potentially removing one of the biggest barriers to more widespread implementation of cardiac CT and empowers serial coronary plaque volume assessment with CT angiography (figure 1).

Multislice computed tomography is a non-invasive technique that can easily detect CAD at its earliest stages reflected by the presence and severity of coronary artery calcification. Minor lesions in the main coronary arteries could be a sign of advanced vascular disease in the microvasculature which may lead to important ischaemia, possibly even influencing the AF substrate. A recent meta-analysis among 30 prospective studies revealed that the presence of calcifications is associated with a three- to four-fold higher risk for mortality and cardiovascular events.

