CCTA is a novel non-invasive imaging test with high diagnostic performance for detection and quantification of anatomic stenosis compared to invasive coronary angiography (ICA) and intravascular ultrasound (IVUS). Beyond stenosis severity, CCTA also permits anatomic quantification of numerous other atherosclerotic plaque characteristics (APCs) (28, 29). These APCs include additional measures of stenosis severity (% diameter stenosis, % area stenosis, minimum luminal diameter [MLD], minimum luminal area [MLA]), plaque composition (non-calcified, calcified, “mixed”; lowest attenuation density; “spotty” calcification); plaque remodeling (positive, negative, intermediate), plaque burden (volume); and plaque location (proximal versus distal; relation to bifurcation). APCs have been described—both by intravascular methods and in studies with CCTA—to exhibit clinical import for plaque stability; and permit discrimination of patients experiencing stable angina versus acute coronary syndromes. We have performed and reported investigations demonstrating the unique value of plaque composition, low attenuation plaque, and coronary arterial remodeling for the identification of patients that exhibit myocardial ischemia and adverse cardiovascular outcome.

Further, we have published several papers related to the diagnostic performance of CCTA for volumetric quantification of coronary artery plaque volume, composition and other APCs; as well as has determined the utility of automated computational-based methods for coronary artery plaque characterization and quantification (30,32). To determine reliability of CT APC evaluation, we identified a high diagnostic accuracy of measured plaque volume by CCTA versus IVUS in 36 patients. In a separate study of 30 patients who underwent 2 CT scans within 200 days the number of plaques, and measured total, calcified plaque (CP) and non-calcified plaque (NCP) volume. Intra-, inter-, and inter-scan agreement for segments with no plaque was 100%. Intraobserver-interscan correlations of total, CP, and NCP volumes ( $r=0.93-0.97$ ,  $p<0.001$  for all), as well as interobserver-interscan correlations were also very good ( $r=0.81-0.96$ ,  $P$  values  $<0.001$ ).

To enhance CT APC evaluation efficiency, reliability and accuracy, our team has developed the first automated computer software algorithm (AutoPlaq) validated against IVUS that enables

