##### 2. Secondary Endpoints

1. To assess incident plaque rates and quantitative changes in different plaque types in patients randomized to warfarin vs. rivaroxaban using CTA, 12 months after an initial evaluation.
2. Evaluation of plaque progression rates and incident plaque rates in subjects treated with warfarin vs. rivaroxaban. In that context, we will:
  - a. determine whether subjects treated with rivaroxaban display slower rates of progression compared to warfarin treated subjects, after control for all CV risk factors and demographics

[figure not shown]
The study design calls for the enrollment of 120 eligible subjects of diverse ethnic population. Given dropout rate, at least 100 patients should be available for final analysis at the conclusion of 52 week follow-up. Baseline examination will include the results of their demographic, coronary risk factor, lab tests, coronary calcium, as well as coronary plaque volume/composition. All participants will be educated on a low-cholesterol diet at entry to the study. Baseline information regarding risk factors for atherosclerotic cardiovascular disease (cigarette smoking status, systemic hypertension, family history of premature atherosclerosis, menopausal and hormone replacement status in women, sedentary lifestyle, current medications, chest pain questionnaire and measures of obesity) will be determined. After randomization, participants will return quarterly (3, 6, 9 and 12 months to assess compliance with medication, and receive an additional supply of medicine. At 52 weeks follow up, coronary calcium and coronary plaque volume/composition will be measured by readers blinded to the randomization and clinical activities, who are not aware of study-group assignments

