## 8. STUDY ASSESSMENTS AND PROCEDURES

### 8.1 Standard Safety Laboratory Panel

Hematology

- Hemoglobin
- Hematocrit
- Red blood cell count
- White blood cell count and differential
- Platelet count

Serum chemistry

- Aspartate Aminotransferase (AST, SGOT)
- Alanine Aminotransferase (ALT, SGPT)
- Alkaline Phosphatase (reflex to GGTP)
- Creatine Kinase (Creatine Phosphokinase) (CK) (CPK) (reflex to troponin)
- Total Bilirubin
- Uric Acid
- Blood Urea Nitrogen (BUN)
- Electrolytes - sodium, potassium, chloride, Total Protein, Albumin
- Serum Creatinine (Scr)

EGFR will be estimated by the method of **Cockcroft-Gault**:

Cockcroft-Gault CrCl =  $(140 - \text{age}) * (\text{Wt in kg}) * (0.85 \text{ if female}) / (72 * \text{Cr})$

The eGFR is expressed in mL/min/1.73m^2

- Females only: urine HCG pregnancy test (HCG minimum sensitivity of 25 IU/L). If a urine HCG test is positive, patient will be excluded

Data to be Collected: Routine demographic and cardiovascular clinical data have been collected for all patients in the study. For CAC, we will collect Agatston and Volume scores, number of lesions and density for each plaque. For CCTA-specific variables, we will quantify and characterize the following APCs by both manual and automated plaque characterization methods:

- Coronary artery plaque volume
- Non-calcified plaque volume
- Calcified plaque volume
- Plaque location
- Plaque length
- Plaque distribution
- Arterial remodeling
- Low attenuation plaque (Hounsfield unit density <30 HU)
- Spotty calcifications

*2b1a. Overview:* In a single session at baseline and followup, after phlebotomy and physical examination, each subject will receive sequential non-contrast followed by contrast scans. The entire scanning procedure will take approximately 30 minutes.

*Screening.* Subjects will be screened for contraindications for beta-blockers and nitroglycerin (PDE5 inhibitors). The desired heart rate for adequate image quality is  $\leq 70$  bpm. If the heart rate is above this level, a beta-blocker will be prescribed. If a beta blocker is contraindicated, a calcium channel blocker will be given instead.

*2b1b. Noncontrast scan:* This will be performed to measure CAC. Patients will be positioned within the scanner with ECG leads, and a rhythm strip will be viewed. After a scout film is obtained, standard calcium scoring imaging will be performed at the end of inspiration.

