*2b3d. Plaque Quantification.* The calculation of the coronary plaque burden and volume will be performed on axial cross sectional images in a blinded fashion. The plaque area of each coronary plaque visualized in at least 2 adjacent slices (reconstructed slice thickness 0.6 mm) will be determined on all affected slices, and plaque volume will be assessed by multiplying the area by the slice thickness. Summing the total plaque per segment will be done, and compared with the subsequent scan in a blinded manner. Plaque burden will be reported in both a semi-quantitative and a quantitative (volumetric) manner; a plaque burden score will be developed to semi-quantitate the plaque in each participant. The AHA 15 segment model of the coronary arteries and visual semi-quantification of coronary artery calcific and non-calcific plaque will be used. Each plaque will be multiplied by 1 for small plaque volume, 2 for medium plaque volume and 3 for large plaque volume. "Plaque Burden Score" (PBS) will be determined by summing the number of evaluable coronary segments with individual plaque scores (maximum score = 45 (score of 3 for all 15 segments)). The "Percent Plaque Score" (%PS) will be calculated by (number of segments with plaque / total number of evaluable segments)  $\times 100$ . Both plaque burden score and percent plaque score will be evaluated as independent variables and compared to other measures in the study, as aforementioned. The protocol for quantitative plaque assessment (volume, in  $\text{mm}^3$ ) is fully described elsewhere (2). For each lesion identified, minimal lumen diameter and minimal lumen area will be determined as elsewhere described.

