## **13. STATISTICAL CONSIDERATIONS**

### Statistical analysis

All analyses will be performed on a full analysis set basis (those who stay in the trial to the follow up scan). For the primary analysis, ITT (defined as all those randomized into the study) will be used. Continuous variables will be expressed as mean and standard deviation; categorical variables expressed as absolute numbers and percentages. Baseline variables will be compared with an independent t-test (two tailed) after performing Levene's test for equality of variances in all normally distributed continuous variables and the Mann-Whitney test (two-tailed) in all not normally distributed variables. Categorical variables will be tested with two-sided Fisher's exact test. An analysis of variance (ANOVA) model with treatment as the main effect will be used to compare the treatment effect of rivaroxaban and warfarin treatment

strategies. For all measures, the analysis of covariance (ANCOVA) model controlling for baseline demographics and baseline CACS values will be performed. Treatment groups also will be compared with respect to incidence rates of adverse events, laboratory abnormalities, bleeding rates, and concomitant medication use. Measurements and change from baseline in coronary artery calcium scores, vital signs (blood pressure and pulse rate), continuous laboratory variables and compliance values will be summarized using descriptive statistics (mean, standard deviation, minimum, median and maximum) by treatment groups and visit. If the interaction of treatment by baseline laboratory values or CACS is significant at the 0.10 level or below, the nature of the interaction will be further explored. Spearman's rank correlation coefficient will be used for testing correlation between the mean Agatston score. All parameters showing a significant univariate relation with an increased coronary Agatston score and those representing a plausible mechanism in terms of calcification [age, VKA duration, left atrium (LA) diameter, statins, angiotensin-converting enzyme (ACE)-inhibitors] will be included as covariates in a logistic regression model (retention level set at 0.1), odds ratios and 95% confidence intervals (CIs) calculated, and results checked for interaction.

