### Sample Size

**Sample Size Estimation.** Sample sizes for each efficacy area have been calculated assuming performance of two-sided 0.05 level tests and 90% power for the primary endpoint and >85% power for the secondary endpoint to detect differences considered clinically meaningful and plausible based on prior studies. We have based sample sizes on at least 90% power in all end points because false negatives could lead to abandoning further study of a treatment that could have a major positive impact on myocardial infarction in this population. The primary endpoint is progression of atherosclerosis after 1 year of treatment with warfarin compared to rivaroxaban as measured by the annualized relative change in the coronary calcium score, as assessed by the Agatston score. The primary endpoint will be the percentage change in CAC from the baseline, which was calculated as follows:  $(CAC \text{ score at 1 year} - CAC \text{ score at baseline}) / CAC \text{ score at baseline} \times 100$ . From multiple 1 year randomized studies in [name] lab, the mean annualized relative change in the Agatston calcium score was  $27.2 \pm 9.5\%$  and on pilot-treatment group, we observed an average change of  $7.5 \pm 4\%$ . Given a 19.7 % annual change difference (27.2% vs. 7.5%) between two groups was observed from primary data, the trial requires 100 in total (50 patients per arm) to attain power of 90% to detect the effect size according to a two-tailed two-sample t-test at a significance level 0.05 (see figure). If we consider the secondary

endpoint (noncalcified plaque volume change), we will have >85% power without drop-off at a two-tailed significance level 0.05 with 120 subjects.

The secondary endpoint is noncalcified plaque volume, using cardiac CTA. Cardiac CTA has been used successfully by [name] to measure progression of atherosclerosis (30-32). In one relevant study, the mean annualized relative change in the non-calcified plaque volume among 62 subjects given statin was -0.037 with a standard deviation of 0.351. This secondary comparison has power of 0.80 to detect an effect size of 0.5, the mean difference in the annualized relative change in the non-calcified plaque volume between the rivaroxaban and warfarin, according to a two sample t-test at a two-tailed significance level 0.05.

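### The ANCOVA for the continuous CT angiography plaque endpoints adjusts for baseline calcium score but not for the endpoint's own baseline; the cost is a small loss of precision, not bias

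*Combined protocol and SAP*

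**What the plan says.** Section 13 (Statistical analysis) gives a treatment-only ANOVA and then one adjusted model for every endpoint: "For all measures, the analysis of covariance (ANCOVA) model controlling for baseline demographics and baseline CACS values will be performed". It does not name the demographics or the dependent variable.

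Section 13 (Sample Size) states that "The secondary endpoint is noncalcified plaque volume, using cardiac CTA", and bases its power on "the mean difference in the annualized relative change in the non-calcified plaque volume between the rivaroxaban and warfarin". Relative change is therefore the scale that the sample-size text plans for.

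Baseline plaque is already collected. The CCTA part of section 2 schedules plaque volume and composition at weeks 0 and 52. Section 4 lists plaque volume in the baseline examination. Section 8 (2b1a) says that, at baseline and follow-up, "each subject will receive sequential non-contrast followed by contrast scans". Under 2b3d, "Summing the total plaque per segment will be done, and compared with the subsequent scan in a blinded manner". The other covariate list, in section 4 under Secondary Endpoints item 2a ("after control for all CV risk factors and demographics"), does not name baseline plaque either.

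**The concern.** When an endpoint is measured before and after treatment, its own starting value is usually the natural covariate. The plan's rule does this for the calcium score but carries the same covariate over to plaque measures taken from a different (contrast) scan. Calcium score can then stand in for baseline plaque only as far as the two are correlated.

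At stake is precision on noncalcified plaque volume, the one secondary endpoint with a power statement, and direct adjustment for chance imbalance in baseline plaque. Because the dependent variable is not named, the size of the loss also depends on how the sentence is read.

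**Working it through.** **1. The plan's own power.** Sample Size gives power 0.80 at an effect size of 0.5, two-sided 0.05, without stating N for that figure. Reading 0.5 as a standardized difference d (an assumption), the two-sample t-test gives 0.775 at 60 per arm (0.782 by normal approximation), and 0.80 needs 64 per arm. At the 100 patients expected for final analysis (section 4), 50 per arm, power is 0.697. If 0.5 were a raw difference with SD 0.351, d = 0.5/0.351 = 1.42 and power exceeds 0.999, which does not match 0.80. The working base is d = 0.5, 50 per arm, 69.7%.

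**2. Inputs for the gain.**
- Interscan correlations of plaque volumes (section 2, CCTA; 30 patients, scans within 200 days): 0.93 to 0.97 same observer, 0.81 to 0.96 between observers.
- SD of annualized relative change: 0.351 (Sample Size).
- Assumed, because the documents give no figure: correlation q between calcium score and baseline plaque 0.3 to 0.7; SD s of log volume 0.6 to 0.8; true change unrelated to baseline; calcium score informative only through baseline plaque (the case least favourable to calcium score).

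**3. Relative change (planned scale).** Take the interscan correlation as the reliability R of log volume. Measurement error then makes change correlate with log baseline by roughly −s(1 − R)/0.351:
- s = 0.6, R = 0.97: −0.6 × 0.03/0.351 = −0.05
- s = 0.8, R = 0.93: −0.8 × 0.07/0.351 = −0.16

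Simulation on the skewed relative-change scale gives −0.05 to −0.17. The residual variance factor is 1 − ρ² with own baseline and 1 − (qρ)² with calcium score; power uses d/√factor.
- ρ = −0.05: the gain is about 0.1 point.
- ρ = −0.17: the factor is 1 − 0.0289 = 0.971 and power is 71.0%; the gain is 1.15, 0.95 and 0.65 points at q = 0.3, 0.5 and 0.7.

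Over the whole anchored range the gain of own baseline over calcium score is 0.1 to 1.2 points by formula and 0.0 to 1.3 by simulation. A second simulation (q = 0.5, 6,000 runs) gave −0.2 to +0.9. For own log baseline plus calcium score against calcium score alone it gave −0.4 to +0.6, with a simulation error of about 0.6 point per power estimate.

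**4. Absolute change (not the planned scale).** With baseline/follow-up correlation r, the factor is (1 + r)/2 with own baseline and 1 − q²(1 − r)/2 with calcium score.

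| r | own baseline | calcium score, q = 0.3 to 0.7 | gain (points) |
|---|---|---|---|
| 0.97 | 70.3% | 69.7–70.0% | 0.3–0.6 |
| 0.93 | 71.2% | 69.8–70.4% | 0.8–1.4 |
| 0.81 | 74.0% | 70.1–71.7% | 2.2–3.9 |

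**5. Follow-up volume as the dependent variable.** Residual variance with calcium score relative to own baseline is (1 − r²q²)/(1 − r²).
- r = 0.81 (r² = 0.6561): 0.941/0.344 = 2.7 at q = 0.3, and 0.679/0.344 = 2.0 at q = 0.7.
- r = 0.97 (r² = 0.9409): 0.915/0.0591 = 15 at q = 0.3, and 0.539/0.0591 = 9 at q = 0.7.

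**6. Bias and imbalance.** In 4,000 simulated trials with complete data, the mean estimate was −0.171 with no covariate, with calcium score, and with calcium score plus own baseline. Type I error was 0.050 to 0.053 in all models tested. The chance difference in baseline plaque has SD √(2/50) = 0.20. At correlations of 0.05 to 0.17 a difference of that size shifts the result by 0.20 × 0.05 = 0.010 to 0.20 × 0.17 = 0.034 SD, which is 2% to 7% of d = 0.5.

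**The case against.** The strongest reply is that relative change already divides by the endpoint's own baseline, so little is left for a covariate to explain. Step 3 bears this out: the gain is close to simulation noise. The 0.81 correlation does not rescue a larger figure on that scale. With s = 0.6 to 0.8 it implies an error variance of change of 2s²(0.19) = 0.14 to 0.24, above the total of 0.351² = 0.123 (a smaller s could fit). The ANCOVA may also be only supportive, since the sample size rests on a t-test, and section 4 calls the sizing exploratory. All of this stands and keeps the severity low. It does not remove the gap: the sentence covers every measure, and nothing elsewhere supplies the missing covariate.

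A reader might infer more than the documents support:
- *Bias.* None arises from the covariate choice under randomization with complete follow-up. Section 13 also mentions analysing only patients who reach the follow-up scan. Dropout that differs by arm and relates to baseline plaque could bias the estimate, but that is a missing-data question.
- *A substantial power gain on relative change.* This needs a much stronger correlation with baseline than measurement error produces here, and no passage gives one.
- *That the omission explains the roughly 70% power.* That figure follows from the assumed effect size and the number of completers.
- *A severalfold loss of precision.* This requires follow-up volume as the outcome. The endpoint is named once as a volume, but the power statements and objectives describe change or progression, which is the likelier reading.

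**Conclusion.** The point holds, at low severity. For continuous CT angiography plaque endpoints, the prescribed ANCOVA adjusts for baseline calcium score and omits an own-baseline value that the trial already plans to collect. The loss is about 0 to 1 power point for noncalcified plaque volume on the planned scale, and up to about 4 points on absolute change at the lowest reported interobserver correlation.

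These sizes rest on d = 0.5, 50 per arm, the assumed q and s, and short-interval reproducibility correlations standing in for one-year ones. The point does not extend to incident plaque, which has no own baseline value. Whether the ANOVA or the ANCOVA decides the primary endpoint is a separate question and adds no weight here. The case for change is that it is nearly free and that naming the dependent variable closes off the one reading under which the loss would be large.

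**What to change.** Add to section 13 (Statistical analysis):

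*For each continuous CTA plaque endpoint, the ANCOVA of change from baseline includes arm, that endpoint's own baseline value (log-transformed for relative change; untransformed for absolute change), baseline CACS, age and sex.*

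State also that incident plaque is outside this rule, and how patients with zero baseline volume are handled. Relative change is itself undefined for them, so log baseline exists for everyone in that analysis.

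The cost is wording only: no new measurement, and no change to the sample size or the primary endpoint. If baseline plaque turns out to be uninformative, the extra covariate costs one degree of freedom. In simulation, keeping both covariates lost 0.7 to 0.8 power point against no adjustment, so under 1 point.

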### CAC and Progression

Multiple studies have been done to demonstrate the feasibility of measuring CAC change at 12 months. Initial studies suggested that treatment with statins was associated with slower progression of CAC. Callister et al.i studied 149 patients. Patients underwent a baseline and follow-up EBT scan at 12 months and serial LDL cholesterol measurements were obtained.

Progression of calcium volume score was seen in all untreated patients (n = 44; mean LDL 147 ± 22 mg/dl) and averaged 52 ± 36% per year. In contrast, the mean yearly calcium volume score change for all treated patients (n = 105; mean LDL 114 ± 23 mg/dl) was 5 ± 28% (p < 0.001 vs. untreated patients). Among the treated patients, 65 individuals attained a LDL level <120 mg/dl (mean LDL 100 ± 17 mg/dl) and showed a net regression of their calcium volume score (-7 ± 22%). In patients who received HMG-CoA reductase inhibitors but maintained an average LDL >120 mg/dl (mean LDL 139 ± 18 mg/dl), the mean yearly calcium volume score progression was 25 ± 22%. Similar one year studies by [name] et al.,ii and Achenbach et al.,iii showed that statin therapy is associated with slowing of progression of coronary calcium.

The BELLES trialiv was a prospective randomized study of 615 postmenopausal and dyslipidemic women randomized after initial CAC scan to atorvastatin 80 mg/day or pravastatin 40 mg/day. A second scan was repeated in 12 months. The attained mean LDL cholesterol level was significantly lower with atorvastatin (94 mg/dl) than pravastatin (129 mg/dl). Nonetheless, the median relative change in the calcium volume score was not different between the two treatment arms (15.1% and 14.3% for atorvastatin and pravastatin, respectively, p = NS).

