##### Study Design:

- a. Design. The study will be a single-center, randomized, open label comparison of Rivaroxaban **20 mg once daily with food** compared to warfarin therapy (INR target 2-3) for 52 weeks on coronary calcium, coronary plaque composition and volume. One hundred ten eligible subjects will be enrolled using a 1:1 ratio. The sample size in this study is based on exploratory considerations.
- b. Randomization and Stratification. Subjects who meet the eligibility criteria will be randomly assigned to receive rivaroxaban or warfarin
- c. **Endpoint Measures**

Primary - Rate of change in coronary calcium

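### Baseline statin use, which the protocol associates with slower calcium progression, is left out of the models that compare the arms on percent change in CAC; the cost is precision, from slight to substantial

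*Combined protocol and SAP*

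**What the plan says.** **Randomisation.** The Study Design item on randomisation and stratification reads only "Subjects who meet the eligibility criteria will be randomly assigned to receive rivaroxaban or warfarin". It names no stratification factor.

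**Treatment comparison.** The Statistical analysis section gives an ANOVA with treatment as the main effect and, for all measures, an ANCOVA "controlling for baseline demographics and baseline CACS values will be performed". Neither is designated as the primary model, and the demographic covariates are not listed. The Sample Size section plans on an unadjusted "two-tailed two-sample t-test at a significance level 0.05".

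**Where statins appear.** The same Statistical analysis section includes statins and duration of vitamin K antagonist (VKA) use among "those representing a plausible mechanism in terms of calcification". It enters them as covariates in a logistic regression for an increased Agatston score, with a retention level of 0.1. It also plans to compare concomitant medication use between arms. The secondary endpoints add control for cardiovascular risk factors, but for plaque progression.

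**Why statins matter.** The section on CAC and Progression reports yearly calcium volume score progression of 52 ± 36% in untreated patients. Against this it sets "the mean yearly calcium volume score change for all treated patients", given as 5 ± 28%.

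**Data.** Baseline information includes "current medications, chest pain questionnaire and measures of obesity".

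**The concern.** The plan identifies statin use as a plausible influence on calcification and then leaves it out of the comparison that answers the primary question. The eligibility criteria do not mention statins, so the trial can be expected to enrol both users and non-users. If the two groups progress at different rates, that difference stays in the residual variance of the ANOVA and, except for any part carried by baseline score or demographics, of the ANCOVA. The confidence interval is then wider, and power lower, than the planned data would allow.

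This matters to the sponsor on its own terms: the Sample Size section justifies high power by the harm of a false negative.

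**Working it through.** **The plan's own figure.** The inputs are "Given a 19.7 % annual change difference (27.2% vs. 7.5%) between two groups", SDs 9.5 and 4, two-sided 0.05, and 50 per arm "to attain power of 90% to detect the effect size".

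- Pooled SD = √((9.5² + 4²)/2) = 7.29.
- n per arm = 2(1.96 + 1.28)² × 7.29²/19.7² = 2.9, so 3; by the t-test, 5.
- With SD 9.5 throughout: 5 per arm, or 7 by the t-test.

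The stated 50 per arm is therefore not reproduced. Fifty per arm at 90% power and a 19.7-point effect corresponds to an SD of about 30.1. That is close to the SDs of 28 and 36 in the background section and far from 9.5 and 4. This conflict is a separate matter, but it decides which SD is sensible below.

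**Inputs for the check.** Statin gap 52 − 5 = 47 points, SDs 28 (treated) and 36 (untreated), from CAC and Progression; effect 19.7 and 50 per arm, from Sample Size. The share of patients on statins, p, is not given and is assumed.

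**Variance with and without statin use in the model.**

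- Within statin groups: p × 28² + (1 − p) × 36². At p = 0.5 this is 1040, SD 32.2.
- Between statin groups: p(1 − p) × 47². At p = 0.5 this is 552.25, SD 23.5.
- Total: 1592.25, SD 39.9. Share explained: 552.25/1592.25 = 0.35.

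**Power of the two-sided t-test, 50 per arm, 47-point gap.**

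| Assumed statin share | SD unadjusted | SD adjusted | Power unadjusted | Power adjusted |
|---|---|---|---|---|
| 25% | 39.8 | 34.2 | 69% | 81% |
| 50% | 39.9 | 32.2 | 69% | 86% |
| 70% | 37.4 | 30.6 | 74% | 89% |
| 80% | 35.2 | 29.8 | 79% | 91% |
| 90% | 32.2 | 28.9 | 86% | 92% |

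At a 50% share, n per arm for 90% power falls from 87 to 57 (normal approximation).

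**Smaller gaps, 50% share, within-group variance 1040.**

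- Gap 10: between-group variance 0.25 × 10² = 25, share explained 25/1065 = 0.02, total SD 32.6. Power is 84.8% unadjusted and 85.6% adjusted.
- Gap 20: between-group variance 0.25 × 20² = 100, share explained 100/1140 = 0.09, total SD 33.8. Power is 82.3% unadjusted and 85.6% adjusted.

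The gain is about 1 to 3 points of power.

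**Chance imbalance is the same cost seen another way.** The SD of the between-arm difference in statin share is √(2p(1 − p)/50) = 0.10 at p = 0.5. A 1-SD imbalance under a 47-point gap moves the arm difference by 4.7 points. The standard error of the arm difference is √(2 × 1040/50) = 6.45 with statin use in the model and √(2 × 1592.25/50) = 7.98 without. Since 6.45² + 4.7² = 41.6 + 22.1 = 63.7 = 7.98², the imbalance is already contained in the unadjusted standard error.

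**VKA duration.** The background section on warfarin gives mean scores of 53, 90 and 236 by increasing duration. These are score levels, not changes. No figure relates duration to progression, so no gain can be computed.

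**The case against.** **The gain may be small.** The 47-point gap compares treated with untreated patients, is not described as randomised, and is on the volume score, whereas the primary endpoint uses the Agatston score. Within the treated patients of the same study, progression ran from −7% to 25% by attained LDL, a spread that a yes/no term cannot capture. This stands: 69% to 86% is an upper illustration. The randomised trial in 615 women cited in the same section found no difference in progression, but it compared two statins and does not speak to statin versus none.

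**With SDs of 9.5 and 4 the omission is immaterial.** That is correct, since power would be near 100%. But those SDs do not yield the plan's own sample size, and a 47-point gap at 50% use would alone imply an SD of 23.5.

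**Part of it is already handled.** The logistic model and the risk-factor control for plaque progression do use such variables. Neither adjusts the comparison of percent change in CAC, so they mitigate little here.

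**Stronger readings that the documents do not support.**

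- A reader might infer that the protocol says warfarin duration drives progression. It reports an association with score level. Baseline CACS, already in the ANCOVA, may carry part of that.
- A reader might infer that the omission biases the result, or that noise and chance imbalance are two separate harms. Randomisation protects the test, and the imbalance is part of the standard error, as shown above.
- A reader might infer that all background cardiovascular drugs are unrestricted. The exclusion criteria limit aspirin dose and the aspirin–clopidogrel combination; it is only on statins that the criteria are silent.
- A reader might take the unstratified randomisation for a defect. Simple 1:1 allocation is acceptable at this size, and stratifying is a preference.

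**Conclusion.** The point holds for baseline statin use and as a matter of precision only. At 50 per arm, a 19.7-point effect and an assumed 50% statin share, adjustment is worth about 17 points of power (69% to 86%) if the background figures carry over in full, and about 1 to 3 points if the gap is 10 to 20 points. The result depends on the statin share and the true gap, neither of which the documents give for this population, and on an outcome SD near 30 rather than the 9.5 and 4 quoted for planning. It also treats statin status as independent of baseline score and demographics; any overlap with covariates already in the ANCOVA would reduce the gain. For VKA duration the documents support no quantified claim. The change is worth making because it costs almost nothing, not because the planned analysis is invalid.

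**What to change.** In the Statistical analysis section, name the ANCOVA as the primary comparison of percent change in CAC. List its covariates: baseline CACS, the specific demographic variables, and baseline statin use (yes/no), taken from the current medications recorded at baseline.

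Use baseline statin status only. Changes after randomisation in an open-label trial may depend on the arm, so summarise them by arm within the planned comparison of concomitant medication use and do not adjust for them.

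VKA duration may be added if it is collected at baseline. The documents plan it as a covariate in the logistic model but do not list its collection, so the source should be stated.

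Stratifying randomisation by statin use is optional, and possible only if randomisation has not started. The covariate can be pre-specified either way, provided this is done before outcome data by arm are seen.

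Cost: one degree of freedom, or two with VKA duration entered as a linear term, and a short text change.
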